6.8 GENERAL OPHTHALMOLOGIC EXAMINATION

6.8.1 Biomicroscopic Evaluation

Frequency and percentage values for the right and left eyes evaluated using biomicroscopy will be listed for 14 visits for the patient group receiving the "Approved Treatment Regimen" and for all available visits for the patient group receiving the "Wait and Extend" treatment regimen. Lids, conjunctiva, cornea, iris, lens, anterior chamber and other assessments will be presented as percentage and frequency values for normal and abnormal assessments for both treatment arms and for both visits.

Frequency and percentage values for the right and left eyes evaluated using ophthalmoscopy will be listed for 14 visits for the patient group receiving the "Approved Treatment Regimen" and for all available visits for the patient group receiving the "Wait and Extend" treatment regimen.

The list of abnormalities identified with color fundus photography will be provided.

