3.1 Study design

This is a randomized controlled, multicenter, 12 month study of Lucentis (ranibizumab) that the consenting patients will participate in a screening period and will be evaluated for their eligibility to enroll the study. After the screening period and the eligibility assessment of the patient, only one eye will be selected / treated as the study eye. After eligibility confirmation at baseline, patients will be randomized into one of the treatment arms as below:

- Arm 1 - Labeled regime arm: Treatment will be given monthly and will be continued until maximum visual acuity is achieved (the patient's visual acuity is stable for three consecutive monthly assessments performed while on ranibizumab treatment). Thereafter patients should be monitored monthly for visual acuity.
- Retreatment criteria:
 - According to this protocol VA stability means BCVA \geq 84 letters (approximate Snellen equivalent of 20/20) or OCT <300 microns in the last 2 consecutive visits or no improvement can be achieved according to the investigators evaluation regarding VA and OCT measures in the last 2 visits . Stable patients do not require reinjection and should be evaluated in the next visit for reinjection.
 - If VA decreases \geq 5 letters compared to previous visit and OCT is >300 microns, patients will be retreated.
 - If VA decreases \geq 5 letters compared to the previous visit or CRT increases >50 microns compared to the previous visit, patients will be retreated.
 - After 3 monthly injections of the investigational drug laser photocoagulation can be administered if VA worsens \geq 10 letters and/or CRT increases >100 microns.
- The interval between two doses should not be shorter than 1 month.
- Arm 2 - Wait and Extend regime arm: Lucentis (ranibizumab) 0.5 mg will be injected subsequently at baseline, month 1 and 2. After the three initial loading doses, patients will be called for the control visits 1 month later. If the visual acuity has reached a stable level and there is no sign of edema on OCT, patients will not receive intravitreal injection and will be called to come back 6 weeks later. The interval is increased by 2 weeks until a maximum of 8 weeks as long as the patient presents as stable regarding visual acuity, central retinal thickness and clinical findings. If there is a negative change, the interval is shortened back to 4 weeks.

Retreatment criteria:

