4.1 Inclusion criteria

Patients eligible for inclusion in this study have to fulfill **all** of the following criteria:

1. Written informed consent must be obtained before any assessment is performed.
2. Male or female patients >18 years of age who have signed an informed consent
3. Patients with Type 1 or Type 2 diabetes mellitus (according to ADA or WHO guidelines) with HbA1c not more than 12.0% at screening (Visit 1). Patients should be on diet, exercise, and/or pharmacological treatment for diabetes.
4. Patients with visual impairment due to focal or diffuse macular edema with center involvement in at least one eye, as demonstrated with color fundus photography, fluorescein angiography and OCT within 28 days of the baseline treatment. If both eyes are eligible, the one with the worse visual acuity, as assessed at Visit 1, will be selected for study treatment unless, based on medical reasons, the investigator deems the other eye the more appropriate candidate for study treatment. The study eye must fulfill the following criteria at Visit 1:
 - BCVA score between 78 and 39 letters, inclusively, using ETDRS-like visual acuity testing charts at a testing distance of 4 meters (approximate Snellen equivalent of 20/32 to 20/160)
 - Decrease in vision is due to DME and not due to other causes, in the opinion of the investigator

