5.5.8 Prohibited Treatment

Any concomitant medications including prescription drugs or over-the-counter preparations used by a patient during the study and until the conclusion of the study participation (except for routine medications given for ocular procedures required by the protocol, i.e. fluorescein, dilating drops, topical antibiotic, topical anesthetic) must be recorded on the Concomitant medications/Significant non-drug therapies CRF including start and stop dates and reason for use.

Laser photocoagulation for DME is permitted only as rescue treatment according to predefined criteria and needs to be

recorded on the Concomitant medications/Significant non-drug therapies CRF

Use of the following treatments is NOT allowed after the start of the study:

- Chronic concomitant therapy with topical ocular corticosteroids
- Other intravitreal medication in the study eye
- Systemic medications known to be toxic to the lens, retina or optic nerve, including Deferoxamine, Chloroquine/ hydroxychloroquine (Plaquenil), Tamoxifen, Phenothiazines and Ethambutol
- Treatment with glitazones during the study.
- Any other investigational drug

The below treatments will be prohibited 30 days before randomisation: verteporfin (Visudyne®), external beam radiation treatment, , submacular surgery or other surgical interventions for DME.

The below treatments will be prohibited 90 days before randomisation: focal laser photocoagulation treatment.

The below treatments will be prohibited 120 days before randomisation: macular laser photocoagulation treatment.

During the study, below treatment will be permitted: Retrobulber anesthesia to prevent eye movements, metochloropamide or other treatments for preventing the nausea due to fluorescein injection and other routine treatments for glaucoma. The patient will also be provided an additional topical antimicrobial medication to use 3 days after the injection which will be used 4 times a day.

If the investigator decided that the other eye (other than the study eye) has a DME lesion or has a new DME lesion occurred during the study which needs treatment, appropriate routine ranibizumab treatment will be applied by the investigator; however any data will not be collected for the other eye. The ranibizumab treatment applied to the other eye will be given by NOVARTIS.

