6.6 Other assessments

Standard Ophthalmological Examination

In each study visit, a standard ophthalmological examination will be performed to both eyes by using a slit lamp for stereoscopic fundus biomicroscopy and indirect stereo ophthalmoscopy. If needed, the pupil will be dilated by eye drops (ex: tropicamide)

Tonometry

In each study visit, tonometry will be performed to measure the intraocular pressure. IOP will be measured before each injection and 60 minutes (± 10 minutes). In any time during the study, if a significant increase in IOP (≥ 30 mm Hg) is seen in a patient, the patient should be followed closely according to the investigator's decision and additional IOP evaluations should be performed. The patient will leave the study site, after 60 minutes if any safety problems are not seen. If any safety problems or a sudden toxicity occurs, the patient will stay at the study site and will be followed according to the investigator's decision.

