6.2 STUDY EYE

Study eyes (Right Eye or Left Eye) of the patients randomized to either of the two treatment regimens will be listed as n and %.

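### Biomicroscopy and ophthalmoscopy are tabulated by right and left eye, so the tables cannot attribute findings to the study eye on the randomised regimen

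*SAP*

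**What the plan says.** SAP 6.8.1 sets out the slit-lamp table as "Frequency and percentage values for the right and left eyes evaluated using biomicroscopy will be listed for 14 visits" in the labelled arm, and for all available visits in the wait-and-extend arm. The ophthalmoscopy table follows the same pattern: "Frequency and percentage values for the right and left eyes evaluated using ophthalmoscopy will be listed for 14 visits". A sentence between them asks for normal and abnormal counts for each anterior-segment structure. It names no eye, but it reads as a continuation of the right/left layout.

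The protocol's unit of treatment is different. Under Protocol 3.1, "only one eye will be selected / treated as the study eye". Protocol 4.1 chooses that eye by acuity, not by side: "If both eyes are eligible, the one with the worse visual acuity, as assessed at Visit 1, will be selected for study treatment", unless the investigator has medical reasons to prefer the other. SAP 6.2 expects study eyes on both sides and counts them: "Study eyes (Right Eye or Left Eye) of the patients randomized". That count is the SAP's only tabulation of the study eye, and it is not crossed with any outcome.

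Both eyes are examined. Protocol 6.6 says that at each visit "a standard ophthalmological examination will be performed to both eyes by using a slit lamp". If the other eye has DME that needs treatment, Protocol 5.5.8 says "appropriate routine ranibizumab treatment will be applied by the investigator". The same sentence adds that no data will be collected for that eye.

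**The concern.** The trial compares the safety as well as the efficacy of two regimens, and the protocol synopsis and section 6.5 name ophthalmic examination as a safety assessment. The question for these tables is what was found in eyes on each assigned regimen. Columns headed right and left do not answer it. A right-eye column contains study eyes of patients treated on the right and fellow eyes of patients treated on the left, and the left-eye column is the mirror image.

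The fellow eyes are not a clean background either. Some may be untreated, and some may receive ranibizumab on a schedule that randomisation did not assign. A finding in a column could therefore come from an eye on the assigned regimen, an eye treated outside it, or an untreated eye, and the table does not say which.

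At stake is how these descriptive tables are read. The primary analysis and the sample size are not involved.

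**Working it through.** The documents give no rate of abnormal findings and no expected right/left split, so there is no figure of the plan's own to reproduce. The check is a comparison of sections followed by mixture arithmetic on assumed values.

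**1. Do the columns mix?** Inputs: one study eye per patient (Protocol 3.1); side not fixed (Protocol 4.1, SAP 6.2); both eyes examined (Protocol 6.6); columns by side (SAP 6.8.1). If both eyes are recorded, a column avoids mixing only if every study eye in the arm is on the same side. With an assumed 50:50 split and the planned 43 patients per arm, that probability is 2 × 0.5^43, about 2 × 10⁻¹³.

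**2. What does each column show?** Let s be the share of an arm's study eyes that are right eyes, p_s the rate of abnormality in study eyes and p_f the rate in fellow eyes, with both eyes of every patient recorded.

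- Right column = s·p_s + (1 − s)·p_f
- Left column = (1 − s)·p_s + s·p_f

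**3. Between-arm difference.** With the same s in both arms and no arm difference in fellow eyes, the difference in a column is the study-eye difference times the share of study eyes in that column. Assume study-eye rates of 20% and 10% (a 10-point difference) and 5% in fellow eyes of both arms:

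| s | Right column | Difference | Left column | Difference |
|---|---|---|---|---|
| 0.4 | 11.0% vs 7.0% | 4 points | 14.0% vs 8.0% | 6 points |
| 0.5 | 12.5% vs 7.5% | 5 points | 12.5% vs 7.5% | 5 points |
| 0.6 | 14.0% vs 8.0% | 6 points | 11.0% vs 7.0% | 4 points |

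With 10% in fellow eyes of both arms the levels change (at s = 0.5, 15% vs 10% in each column), but the differences stay at 4 to 6 points.

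**4. Excess of study over fellow eyes within an arm.** Assume 12% and 4%. At s = 0.5 both columns show 0.5 × 12 + 0.5 × 4 = 8%, and the excess cannot be seen. At s = 0.4 the right column shows 7.2% and the left 8.8%; at s = 0.6 these are reversed.

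**5. Unequal split between arms.** With the same 12% and 4% in both arms but s = 0.6 in one and 0.4 in the other, the right column shows 8.8% vs 7.2% although the arms do not differ.

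**6. Can the study-eye result be recovered?** Adding the two columns gives p_s + p_f for the arm, and adding the two between-arm differences gives the study-eye difference plus the fellow-eye difference. The total is kept; the separation is not.

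**7. Does another section supply it?** SAP 6.12 also tabulates FFA by right and left eye. SAP 6.9 and 6.11 report BCVA and central thickness for both eyes, and SAP 6.10 names no eye for IOP. Protocol 9.5.2 asks for safety summaries per visit and arm only. None gives the 6.8.1 findings by study eye.

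**The case against.** The strongest reply is that nothing is hidden. Both columns are printed, and every study-eye abnormality is counted in one of them. In the example above, the column differences add to the full 10 points. Complications should also reach the report as adverse events: Protocol 7.1 allows them to be detected by examination, Protocol 9.5.2 summarises them by arm and system organ class, and SAP 6.15.1 lists them with severity, relationship and action taken. The 6.8.1 tables carry no test or decision rule.

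Most of this stands. A reader might infer that the tables would conceal a safety problem or falsely reassure; the documents do not support that, because adverse events are reported separately. What remains is attribution. The column sum equals the study-eye difference only if fellow eyes do not differ between arms, which cannot be assumed when they may be treated. Nor do the adverse-event fields named in Protocol 7.1 and SAP 6.15.1 include the affected eye.

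Two other stronger readings also fail. One is that all ocular safety tables have this fault. Among the safety examinations, the explicit right/left layout covers biomicroscopy and ophthalmoscopy only; the IOP gap is an unstated eye, and Protocol 6.4 places FFA under efficacy. The other is that study versus fellow means injected versus uninjected, which Protocol 5.5.8 rules out.

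Finally, mixing in every column cannot be asserted outright while Protocol 5.5.8 says that no other-eye data will be collected. If that covers only the details of fellow-eye treatment, the columns mix. If treated fellow eyes drop out of the data, the columns mix study eyes with untreated fellow eyes only. If no fellow-eye findings are kept at all, nothing mixes, but study eyes are split by a side that has no bearing on the comparison. A study-eye table is better under each reading.

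**Conclusion.** The point holds as a defect of specification in descriptive safety tables. Where both eyes are recorded, SAP 6.8.1 as written pools study and fellow eyes, and its tables cannot attribute examination findings to the assigned regimen. Any excess or arm difference confined to study eyes is reduced in each column in proportion to the share of study eyes there, to about half at an even split.

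The 4-to-6-point figure rests on assumed rates, a study-eye share of 40 to 60% that is the same in both arms, no arm difference in fellow eyes, and both eyes recorded for every patient. The documents supply none of the rates and no actual split. The direction of the dilution does not depend on the particular rates, provided the excess lies in study eyes. The point is worth correcting because the remedy is simple; it does not show that events would go unreported.

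**What to change.** In SAP 6.8.1, replace the right/left breakdown with study eye and fellow eye for both biomicroscopy and ophthalmoscopy, using the laterality already recorded for SAP 6.2, and say that the anterior-segment sentence follows the same layout. Make the study-eye table, by arm and visit, the main ocular examination table. Show fellow eyes separately, with a note that they may have received ranibizumab outside the randomised regimen and are not uninjected controls.

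Reconcile the statement in Protocol 5.5.8 that no data will be collected for the other eye with the both-eye examinations in Protocol 6.6, and state which fellow-eye findings enter the tables. For consistency, name the eye for IOP in SAP 6.10 and use the same layout for FFA in SAP 6.12.

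The cost is a change of SAP wording and the matching table programming. No new examination is needed and the sample size is unchanged. Splitting fellow eyes further into treated and untreated would need fellow-eye treatment data, which Protocol 5.5.8 may exclude, so that split should be planned only if the data exist.

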6.9 BCVA (BEST CORRECTED VISUAL ACUITY) – FROM 4 METERS WITH ETDRS

Descriptive statistics (n, mean, standard deviation, minimum, median, maximum and 95% confidence interval) for BCVA Test scores applied to both eyes will be tabulated for all 14 visits for the patient group receiving the “Approved Treatment Regimen” and until the last available visit for the patient group receiving the “Wait and Extend” treatment regimen. For both treatment groups, the change between the first and final visits will be compared using the t-test for paired sequences or Wilcoxon Signed Rank Test based on the fit of the data to normal distribution.

6.10 INTRAOCULAR PRESSURE (IOP) EXAMINATIONS

Descriptive statistics (n, mean, standard deviation, minimum, median, maximum and 95% confidence interval) for Intraocular Pressure values will be collected for all 14 visits for the patient group receiving the “Approved Treatment Regimen” and until the last available visit for the patient group receiving the “Wait and Extend” treatment regimen.

6.11 OPTICAL COHERENCE TOMOGRAPHY

The device used for OCT will be listed together with n and % values for both treatment arms. Frequency (n) and percentage (%) values for the options describing the results of intraretinal edema involving the macula (Yes, No, Not evaluated) will be tabulated for both groups. Type of the edema, if applicable, will also be tabulated using frequency and % values.

Descriptive statistics (n, mean, standard deviation, minimum, median, maximum and 95% confidence interval) for central thickness values for both eyes will be listed separately for each of the treatment arms.

Frequency (n) and percentage (%) values for the options describing subretinal fluid results (Yes, No, Suspected, Not evaluated) and the options describing results of vitreoretinal interface changes (Yes, No) will be tabulated for both eyes. Frequency (n) and percentage (%) values for the options, i.e. vitreoretinal traction, epiretinal membrane and macular hole will also be listed for patients with vitreoretinal interface changes.

6.12 FLUORESCEIN FUNDUS ANGIOGRAPHY (FFA)

For the results of FFA performed compulsorily at the first and month 12 visits and at investigator discretion during other visits, answers describing presence of diabetic macular edema (Yes, No) will be individually listed as frequency (n) and percentage (%) values for the right and left eyes in each of the treatment arms, and frequency (n) and percentage (%) values for the specified “Focal” and “Diffuse” options will be listed for those with the “Yes” answer. Yes and No answers to macular ischemia and peripheral ischemia questions will be individually listed as frequency (n) and percentage (%) values for the right and left eyes in each of the treatment arms. For Yes, No and Suspected answers to another condition identified with FFA, frequency (n) and percentage (%) values will be tabulated, and the details provided for the Yes answers will be provided.

The rates of diabetic macular edema, macular ischemia, peripheral ischemia and other conditions identified with FFA will be compared during the first and month 12 visits using the Mc Nemar test.

6.13 CONCOMITANT MEDICATIONS / TREATMENTS

Yes or No answers to whether patients were receiving concomitant medications / treatments will be listed as frequency (n) and percentage (%) values for both treatment groups.

The medications used by the patients receiving concomitant medications / treatments will be grouped and listed.

6.14 EFFICACY EVALUATION

6.14.1 Visual Acuity

In order to demonstrate that the “wait and extend” regimen of ranibizumab is non-inferior to the posology described in the prescribing information, mean change in BCVA at month 12 from the baseline visit will be determined for both treatment groups, and a comparison will be made between the two groups using the Mann Whitney u test.

The number of patients with improvement in BCVA from baseline will be compared for the two treatment groups using the Chi-Square test (with Fisher’s Exact Test where appropriate).

The number of patients with improvement of 5 or more letters from baseline will be compared for the two treatment groups using the Chi-Square test (with Fisher’s Exact Test where appropriate).

The number of patients with improvement of 10 or more letters from baseline will be compared for the two treatment groups using the Chi-Square test (with Fisher's Exact Test where appropriate).

The number of patients with improvement of 15 or more letters from baseline will be compared for the two treatment groups using the Chi-Square test (with Fisher's Exact Test where appropriate).

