9.2 Patient demographics and other baseline characteristics

Descriptive statistics for continuous variables (i.e.: N, mean, standard deviation, median, maximum and minimum) and frequency and percent ranges for categorical variables will be given. Demographic data of the patients (including height and weight) and baseline visual acuity will be submitted as summary tables. Medical history and ocular medical history will be summarized per treatment arms.

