9.4.2 Statistical model, hypothesis, and method of analysis

There is no special hypothesis intended for this study.

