9.4.4 Supportive analyses

Not applicable.

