6.14.2 Optical Coherence Tomography

The mean change from baseline to month 12 in Central Retinal Thickness determined with Optical Coherence Tomography for both eyes will be calculated for both groups and will be compared using the Mann Whitney u test.

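### The between-arm comparisons of month-12 BCVA and CRT change do not adjust for baseline, so the plan passes up precision that would cost nothing

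*SAP*

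**What the plan says.** SAP 6.14.1 states that "mean change in BCVA at month 12 from the baseline visit will be determined for both treatment groups" and that "a comparison will be made between the two groups using the Mann Whitney u test". No covariate is named.

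SAP 6.14.2 treats retinal thickness the same way. "The mean change from baseline to month 12 in Central Retinal Thickness" is to be obtained by OCT "for both eyes will be calculated for both groups and will be compared using the Mann Whitney u test". This too is unadjusted, and it is written for both eyes rather than the study eye.

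The protocol adds no model. Section 9.4.2 says only "There is no special hypothesis intended for this study", and section 9.4.4 on supportive analyses reads "Not applicable". In section 9.2 the only use of the baseline measurement is that "baseline visual acuity will be submitted as summary tables".

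Allocation in Protocol 5.3 is 1:1, and no stratification by baseline BCVA or CRT is described. Entry acuity is wide: Protocol 4.1 admits a study eye with a "BCVA score between 78 and 39 letters, inclusively".

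**The concern.** In a trial of this size the arms can differ at baseline by chance. A change score subtracts each patient's baseline, but it does not remove the association between baseline and subsequent change. If eyes that start lower tend to gain more, the arm that happens to start lower looks better than it should. Across repeated trials this averages out. In the one trial that is run, it can move the estimate towards or away from the 5-letter margin.

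An association of this kind is plausible. The entry range is wide, and when both eyes qualify the one with the worse acuity at Visit 1 is normally chosen, which invites regression to the mean. Adjusting for baseline would remove that part of the imbalance and reduce the residual variance. The study is open-label and no supportive analysis is planned, so an adjustment introduced after an imbalance has been seen would be post hoc.

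**Working it through.** **Inputs.** From Protocol 9.7 and SAP 5.1: margin 5 letters, SD of change 7 letters, significance level 0.025, 43 evaluable patients per arm. The SD is stated for the labelled arm and is taken here as common to both arms. The true difference is not stated and is taken as 0. The correlation r between baseline and change is not in the documents, so it is an assumption shown over a range.

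**The plan's own figure.** The standard error of the unadjusted difference is 7 × √(2/43) = 1.51 letters, and the noncentrality is 5/1.51 = 3.31. A one-sided 0.025 t-test with 84 degrees of freedom then has 90.6% power, and 43 is the smallest number per arm that reaches 90%. The normal approximation gives 42. Reading 0.025 as two-sided would need 49, so the level is one-sided. The stated size of 86 is reproduced.

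**Effect of adjustment.** With baseline as a covariate:

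- Residual SD = 7 × √(1 − r²), with 83 degrees of freedom.
- Variance reduction = r².
- Equivalent increase in patients = 1/(1 − r²) − 1.

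**Imbalance left in a change-score difference.** The slope of change on baseline is r × 7/SD(baseline). A 1.96-SD chance imbalance is 1.96 × SD(baseline) × √(2/43). In the product the baseline SD cancels, leaving 1.96 × r × 7 × √(2/43) = 2.96 × r letters.

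| Size of r (assumed) | Residual SD | Power, 43 per arm | Variance reduction | Equivalent extra patients | Shift from 1.96-SD imbalance | Share of margin |
|---|---|---|---|---|---|---|
| 0 (unadjusted t-test) | 7.00 | 90.6% | – | – | 0 | 0% |
| 0.1 | 6.96 | 90.8% | 1% | 1% | 0.30 | 6% |
| 0.2 | 6.86 | 91.6% | 4% | 4% | 0.59 | 12% |
| 0.3 | 6.68 | 92.9% | 9% | 10% | 0.89 | 18% |
| 0.5 | 6.06 | 96.6% | 25% | 33% | 1.48 | 30% |

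The half-width of the 95% CI falls from 3.00 letters unadjusted to 2.86 at 0.3 and 2.60 at 0.5.

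**Which r is plausible.** If acuity has the same SD at baseline and month 12 (an assumption), |r| = 7/(2 × baseline SD). Baseline SDs of 8, 10 and 12 letters give 0.44, 0.35 and 0.29.

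**Simulation.** This used 40,000 trials per scenario with 43 per arm, an assumed SD of 10 letters at baseline and month 12 (|r| = 0.35), and every test shifted by the 5-letter margin.

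- No true difference: power is 90.6% for the t-test on change, 89.2% for Mann-Whitney and 93.7% for ANCOVA.
- True deficit of 5 letters: the false non-inferiority rate is 2.6% for all three.
- Same deficit, in the 5% of trials where wait-and-extend starts lowest: about 10% on change scores, 2.8% with ANCOVA.
- No true difference, in the 5% where wait-and-extend starts highest: power is 73% (t-test) or 71% (Mann-Whitney), against 93% with ANCOVA.

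**CRT.** The documents give no SD or correlation for CRT, so no corresponding figure can be derived.

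**The case against.** The strongest reply is that nothing here is broken. The trial was sized on the SD of change, so an unadjusted comparison of changes already has the planned power, and randomisation keeps overall type I error at its nominal level. This stands. A reader might infer that the primary analysis is biased or underpowered for want of a covariate; the plan's own figures do not support that.

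A reader might also infer that a chance baseline difference carries over in full to the treatment difference. It does not. Change scores remove part of it, and what remains is proportional to r. At r = 0 nothing remains, and at 0.1 to 0.2 the power gain is at most one percentage point.

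A third tempting step is to treat the 84-letter criterion in Protocol 3.1 as proof that change is tied to baseline, since it lies 6 letters above the top of the entry range and 45 above the bottom. That criterion is only one of three alternative routes to stability. The others are an OCT value below 300 microns and the investigator's judgement that no further improvement can be achieved. It governs re-injection and does not cap measurable acuity. A correlation is plausible, but the text does not establish it.

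Finally, SAP 6.14.1 defines no between-arm difference, no confidence interval and no use of the 5-letter margin. That is a larger and separate defect. It does not make this point redundant, because an interval added later could still be unadjusted.

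**Conclusion.** The plan misses an inexpensive gain in precision and in robustness to an unlucky allocation. On the text the omission is clear: neither document contains a baseline-adjusted comparison or describes allocation stratified by baseline.

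Its importance rests on an r that the documents do not supply. The gain is negligible at 0.1, small at 0.2 and worthwhile from about 0.3. The benefit is mostly conditional: it matters when the arms happen to differ at baseline, and that cannot be known when the SAP is written. The power figures assume a common SD of 7 letters, no true difference and a t-based comparison. They do not describe the planned Mann-Whitney test, which as written carries no margin. For CRT the direction of the argument is the same, but its size is unknown.

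**What to change.** In SAP 6.14.1, estimate the arm difference in month-12 BCVA change in the study eye by ANCOVA, with treatment arm and continuous baseline BCVA as terms. Report the adjusted difference (wait-and-extend minus labelled) with its two-sided 95% CI, and compare the lower limit with −5 letters. Keep the unadjusted comparison as supportive.

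Define baseline. The Protocol section 6 schedule places BCVA at Visits 1 and 2, Protocol 6.2 says assessments completed at Visit 1 should not be repeated at Visit 2, and SAP 6.9 works from the first visit whereas 6.14.1 refers to the baseline visit. State which pre-injection value is used, and what happens when only one exists.

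In SAP 6.14.2, use the same model for study-eye CRT with baseline CRT as the covariate. Before the first injection, OCT is scheduled only at Visit 1.

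The cost is SAP wording and one covariate definition. No extra patients, visits or measurements are needed.
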